#### **5.2.2.7 Clinical – Global Impression of Change (CGIC) assessment**

The Clinical Global Impression of Change (CGIC) instrument is used to evaluate the overall response to treatment. The investigator (clinician) will be asked to rate the degree to which the overall asthma status may have changed when compared to baseline (i.e. randomization visit/initiation of study drug). The assessment uses a 7-point rating scale: 1 = Very Much Improved; 2 = Much Improved; 3 = Minimally Improved; 4 = No Change; 5 = Minimally Worse; 6 = Much Worse; and 7 = Very Much Worse.

The CGIC will be completed at the site visits as indicated in [Table 1](#). It is recommended that the same clinician completes the CGIC at all applicable visits for an individual subject. Before making the assessment the clinician will need to access and review the results from all relevant assessments including lung function measurements (FEV1 and PEF) and patient reported outcomes (Asthma Daily Diary, ACQ-6 and AQLQ) performed before the visit, Adherence to the patient reported outcomes should be closely monitored.

### **5.3 Pharmacokinetics and Immunogenicity**

#### **5.3.1 Collection of samples**

Blood samples for determination of tralokinumab in serum will be collected pre-dose at the times presented in [Table 1](#). It is important that date and time of each SC injection and sample collection be recorded for each subject.

Instructions for sample collection, labelling, processing, storage, and shipment will be provided in a separate laboratory manual provided to the sites.

The volume of blood that will be collected from each subject for these assessments is presented in [Table 6](#).

### **5.3.2 Determination of drug concentration**

Samples for determination of tralokinumab concentration in serum will be analyzed by a laboratory on behalf of AstraZeneca, using a validated bioanalytical method. Details of the analytical method used will be described in a bioanalytical report. The PK samples will be retained for future use at AstraZeneca, or designee, for a maximum of 15 years following the date of Last Subject Last Visit.

A summary of PK analysis results will be reported in the CSR; details of the PK analysis will be reported separately in a bioanalytical report.

### **5.3.3 Storage and destruction of pharmacokinetic samples**

Pharmacokinetic samples may be disposed of or destroyed and anonymized by pooling. Additional analyses may be conducted on the anonymized, pooled pharmacokinetic samples to further evaluate and validate the analytical method. Any results from such analyses may be reported separately from the CSR.

Incurred sample reproducibility analysis, if any, will be performed alongside the bioanalysis of the test samples. The results from the evaluation will not be reported in the Clinical Study Report but separately in a Bioanalytical Report.

Any residual back-up PK samples may be used for future exploratory biomarker research (in this case, residual back-up PK samples will be shipped to the AstraZeneca Biobank; see details in the Laboratory Manual).

### **5.3.4 Immunogenicity**

Instructions for immunogenicity (ADA and nAb) sample collection, processing, storage, and shipment will be provided in a separate laboratory manual provided to the sites.

Samples used for immunogenicity analyses will be retained at AstraZeneca or designee for a maximum of 15 years following the Last Subject's Last Visit. A summary of the analysis will be presented in the CSR. Details of the analytical method used will be described in a bioanalytical report.

### **Anti-tralokinumab antibodies**

The pre-dose serum samples to measure presence of ADA will be collected according to the schedule of study procedures (see [Table 1](#)).

The presence or absence of ADA will be determined in the serum samples using a validated bioanalytical method. A tiered testing scheme will be employed, with the first step being screening. Samples found positive in the screening step will be tested in the confirmatory step.

Samples confirmed positive for ADA in the confirmatory step will undergo endpoint titer determination and will be analyzed for the presence of nAb.

## Neutralizing antibodies

Neutralizing antibodies will be assessed at Visits 3, 16, 30, 31 and IPD according to the tiered testing scheme outlined above.

The presence or absence of nAb will be determined using a validated bioanalytical method. A summary of nAb incidence rate will be reported in the CSR and details of the nAb assessment will be reported separately in a bioanalytical report.

### 5.3.5 Total IgE

Testing for total IgE will be performed at Visits 3, Visit 9 and Visit 29 (Weeks 0, 12 and 52, respectively).

Instructions for sample collection, processing, storage, and shipment will be provided in a separate laboratory manual provided to the sites.

### 5.3.6 Phadiatop®

Testing for phadiatop® will be performed at Visit 3 (Week 0). The analysis for these will be performed by central laboratory. Instructions for sample collection, processing, storage, and shipment will be provided in a separate laboratory manual provided to the sites.

## 5.4 Pharmacodynamics

### 5.4.1 Serum biomarkers

Blood (serum) samples will be collected pre-dose according to the schedule in [Table 1](#) to evaluate the pharmacology of tralokinumab, including but not limited to, periostin and DPP4.

The periostin level measured at Visit 2 will also be used for stratification at randomization.

Instructions for sample collection, processing, storage, and shipment will be provided in a separate laboratory manual provided to the sites. AstraZeneca or a designee will retain serum biomarker samples for investigation of the pharmacology of tralokinumab for a maximum of 15 years following the last subject's last visit.

The results from the investigation of such samples may not be reported in the CSR but in separate reports and in scientific publications as appropriate.

## 5.5 Pharmacogenetics

### 5.5.1

[REDACTED]

[REDACTED]

[Redacted]

[Redacted]

[Redacted]

### 5.5.2 Storage, re-use and destruction of pharmacogenetic samples

[Redacted]

[Redacted]

[Redacted]

### 5.6 Biomarker analysis

The subject's consent or assent to the use of donated biological samples for non-exploratory analysis purposes is mandatory.

Biological samples (i.e., blood, plasma, serum) will be collected and may be analyzed for exploratory biomarkers to assess correlations with disease activity, effects of study drug, clinical outcomes and toxicity.

### **5.6.1 Storage, re-use and destruction of biological samples**

Samples will be stored for a maximum of 15 years from the date of the Last Subject's Last Visit, after which they will be destroyed. The results of this biomarker research will be reported either in the Clinical Study Report itself or as an addendum, or separately in a scientific report or publication. The results of this biomarker research may be pooled with biomarker data from other studies with the study drug to generate hypotheses to be tested in future research.

### **5.6.2 Labelling and shipment of biological samples**

The Principal Investigator will ensure that samples are labelled and shipped in accordance with the Laboratory Manual and the Biological Substance, Category B Regulations (materials containing or suspected to contain infectious substances that do not meet Category A criteria), see Appendix C 'IATA 6.2 Guidance Document'.

Any samples identified as Infectious Category A materials will not be shipped and no further samples will be taken from the subject unless agreed with AstraZeneca, and appropriate labelling, shipment and containment provisions are approved.

### **5.6.3 Chain of custody of biological samples**

A full chain of custody will be maintained for all samples throughout their lifecycle.

The Principal Investigator, or delegate, at each site will keep full traceability of collected biological samples from the subjects while in storage at the site until shipment or disposal (where appropriate), along with documentation of receipt of arrival.

The sample receiver will keep full traceability of the samples while in storage and during use until used, or disposed of, or until further shipment along with documentation of receipt of arrival.

AstraZeneca will keep oversight of the entire life cycle through internal procedures, monitoring of study sites, and auditing of external laboratory providers.

Samples retained for further use will be registered in Fisher Bioservices or designate during their entire life cycle.

### **5.6.4 Withdrawal of Informed Consent or Assent for donated biological samples**

If a subject withdraws consent or assent to the use of their donated biological samples that will be used for non-exploratory purposes, the samples will be disposed of/destroyed, and the action documented. If samples are already analyzed, AstraZeneca is not obliged to destroy the results of this research. As collection of the biological samples that will be used for non-exploratory purposes, is an integral part of the study, the subject will be withdrawn from further study participation. Subjects who withdraw their consent/assent for the use of their samples to be used for exploratory/future use purposes, will be allowed to continue in the study.

The Principal Investigator will be responsible for ensuring that:

- The subject's withdrawal of informed consent or assent to the use of donated samples is notified immediately to AstraZeneca
- The biological samples from any subject who withdraws consent or assent to the use of these samples, if stored at the study site, are immediately identified, disposed of /destroyed, and the action documented
- The laboratory (ies) holding the samples is/are informed about the withdrawn consent or assent immediately, and that samples are disposed of/destroyed, the action documented, and the signed document returned to the study site
- The subject and AstraZeneca are informed about the sample disposal

AstraZeneca will ensure that the central laboratory (ies) holding the samples is/are informed about the withdrawn consent or assent immediately, the samples are disposed of/destroyed, and that the action is documented and provided to the study site.

## **6. SAFETY REPORTING AND MEDICAL MANAGEMENT**

The Principal Investigator is responsible for ensuring that all staff involved in the study are familiar with the content of this section.

### **6.1 Definition of adverse events**

An AE is the development of an undesirable medical condition or the deterioration of a pre-existing medical condition following or during exposure to a pharmaceutical product, whether or not considered causally related to the product. An undesirable medical condition can be symptoms (e.g., nausea, chest pain), signs (e.g., tachycardia, enlarged liver) or the abnormal results of an investigation (e.g., laboratory findings, electrocardiogram). In clinical studies, an AE can include an undesirable medical condition occurring at any time, including run-in or washout periods, even if no study treatment has been administered.

The term AE is used to include both serious and non-serious AEs.

### **6.2 Definitions of serious adverse event**

An SAE is an AE occurring during any study phase (i.e., run-in, treatment, washout, follow-up), that fulfils one or more of the following criteria:

- Results in death
- Is immediately life-threatening

- Requires in-subject hospitalization or prolongation of existing hospitalization
- Results in persistent or significant disability/incapacity or substantial disruption of the ability to conduct normal life functions
- Is a congenital abnormality or birth defect
- Is an important medical event that may jeopardise the subject or may require medical intervention to prevent one of the outcomes listed above.

For further guidance on the definition of a SAE, see Appendix B to the Clinical Study Protocol.

### **6.3 Recording of adverse events**

#### **6.3.1 Time period for collection of adverse events**

Adverse Events, including SAEs will be collected from the time the subject signs the informed consent or assent form, throughout the treatment period and the follow-up periods (i.e., Visit 30, (Week 56) and Visit 31, (Week 72)).

#### **6.3.2 Follow-up of unresolved adverse events**

Any AEs that are unresolved at any follow up visit in the study will be followed up by the Investigator for as long as medically indicated, but without further recording in the CRF. AstraZeneca retains the right to request additional information for any subject with ongoing AE(s)/SAE(s) at the end of the study, if judged necessary.

#### **6.3.3 Adverse event variables**

The following variables will be collected in the eCRF for each AE:

- AE (verbatim)
- The date when the AE started and stopped
- Maximum intensity\* of the AE
- Whether the AE is serious or not
- Investigator causality rating against the Investigational Product (yes or no)
- Action taken with regard to IP
- AE caused subject's withdrawal from study (yes or no)
- Outcome

\*Intensity rating scale:

- 1 mild (awareness of sign or symptom, but easily tolerated)
- 2 moderate (discomfort sufficient to cause interference with normal activities)

- 3 severe (incapacitating, with inability to perform normal activities)

In addition, the following variables (if applicable) will be collected in the eCRF for SAEs:

- Date AE met criteria of serious
- Date Investigator became aware of the SAE
- AE is serious due to
- Date of hospitalization
- Date of discharge
- Probable cause of death
- Date of death
- Autopsy performed
- Causality assessment in relation to Study procedure(s)
- Description of the AE

It is important to distinguish between serious and severe AEs. Severity is a measure of intensity, whereas seriousness is defined by the criteria in Section 6.2. An AE of severe intensity need not necessarily be considered serious. For example, nausea that persists for several hours may be considered severe nausea, but not a SAE unless it meets the criteria shown in Section 6.2. On the other hand, a stroke that results in only a limited degree of disability may be considered a mild stroke but would be a SAE when it satisfies the criteria shown in Section 6.2.

#### 6.3.4 Assessment of causality

The Investigator will assess causal relationship between Investigational Product and each Adverse Event, and answer 'yes' or 'no' to the question 'Do you consider that there is a reasonable possibility that the event may have been caused by the investigational product?'

For SAEs causal relationship will also be assessed for other medication and study procedures. **Note** that for SAEs that could be associated with any study procedure the causal relationship is implied as 'yes'.

A guide to the interpretation of the causality question is provided in Appendix B to the Clinical Study Protocol.

#### 6.3.5 Adverse events based on signs and symptoms

All AEs spontaneously reported by the subject or reported in response to the open question from the study personnel: '*Have you/your child had any health problems since the previous visit/you were last asked*', or revealed by observation will be collected and recorded in the CRF. When collecting AEs, the recording of diagnoses is preferred (when possible) to recording a list of signs and symptoms. However, if a diagnosis is known and there are other

signs or symptoms that are not generally part of the diagnosis, the diagnosis and each sign or symptom will be recorded separately.

### **6.3.6 Adverse events based on examinations and tests**

The results from protocol mandated laboratory tests and vital signs will be summarized in the CSR. Deterioration as compared to baseline in protocol-mandated laboratory values and vital signs should therefore only be reported as AEs if they fulfil any of the SAE criteria or are the reason for discontinuation of treatment with the IP.

If deterioration in a laboratory value/vital sign is associated with clinical signs and symptoms, the sign or symptom will be reported as an AE and the associated laboratory result/vital sign will be considered as additional information. Wherever possible the reporting Investigator will use the clinical, rather than the laboratory term (e.g., anaemia versus low haemoglobin value). In the absence of clinical signs or symptoms, clinically relevant deteriorations in non-mandated parameters should be reported as AE(s).

Deterioration of a laboratory value, which is unequivocally due to disease progression, should not be reported as an AE/SAE.

Any new or aggravated clinically relevant abnormal medical finding at a physical examination as compared with the baseline assessment will be reported as an AE.

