### **6.3.8 Disease progression**

#### **Symptoms of the disease under study**

Asthma symptoms or signs, such as wheeze, cough, chest tightness, dyspnoea, breathlessness and phlegm, will be recorded as AEs when:

- the sign or symptom is serious according to definitions, see Section 6.2,
- the subject discontinues the study due to the sign or symptom, and/or
- the sign or symptom is new to the subject or not consistent with the subject's pre-existing asthma history (defined as within 1 year of Visit 1 as judged by the investigator).

Asthma exacerbations should not be recorded as AEs after randomization, unless it fulfils any of the above criteria. All asthma exacerbations should be recorded in the exacerbation eCRF as per section 5.1.1.

If a subject discontinues IP due to a study specific discontinuation criterion, this should always be recorded as 'Development of study specific withdrawal' on the termination form in the eCRF. In addition, the investigator must assess whether the asthma deterioration should also be reported as an AE leading to discontinuation of IP (DAE)/AE leading to withdrawal from study on the AE form.

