## 6.4 Reporting of serious adverse events

All SAEs must be reported, whether or not considered causally related to the IP, or to the study procedure(s). All SAEs will be recorded in the eCRF.

If any SAE occurs during the course of the study, Investigators or other site personnel must inform the appropriate AstraZeneca representatives within one day (i.e., immediately) but **no later than 24 hours** of when he or she becomes aware of it.

The designated AstraZeneca representative will work with the Investigator to ensure that all the necessary information is provided to the AstraZeneca Subject Safety data entry site **within 1 calendar day** of initial receipt for fatal and life threatening events **and within 5 calendar days** of initial receipt for all other SAEs.

For fatal or life-threatening AEs where important or relevant information is missing, active follow-up will be undertaken immediately. Investigators or other site personnel must inform AstraZeneca representatives of any follow-up information on a previously reported SAE within 1 calendar day (i.e., immediately) but no later than 24 hours of when he or she becomes aware of it.

Once the Investigators or other site personnel indicate an AE is serious in the WBDC system, an automated email alert will be sent to the designated AstraZeneca representative(s).

If the WBDC system is not available, then the Investigator or other study site personnel reports a SAE to the appropriate AstraZeneca representative(s) by telephone.

The AstraZeneca representative(s) will advise the Investigator/study site personnel how to proceed.

The reference document for definition of expectedness/listedness is the Investigator's Brochure for the AstraZeneca IP.

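### Section 6.3.6 bars reporting of laboratory deterioration attributed to disease without exempting serious or treatment-stopping changes, against section 6.4 and its own first paragraph

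*Protocol*

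**What the plan says.** Protocol section 6.3.6 gives two rules that bear on laboratory values.

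- Its first paragraph deals with protocol-mandated laboratory tests and vital signs. Because these results are summarised in the study report anyway, a deterioration should "only be reported as AEs if they fulfil any of the SAE criteria or are the reason for discontinuation of treatment with the IP".
- A later, free-standing sentence applies to laboratory values in general: "Deterioration of a laboratory value, which is unequivocally due to disease progression, should not be reported as an AE/SAE". It names SAEs explicitly and has no exception.

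Between the two, the section says that when a laboratory change comes with clinical signs or symptoms, "the sign or symptom will be reported as an AE and the associated laboratory result/vital sign will be considered as additional information".

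The surrounding sections set the frame:

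- Section 6.1 counts as an AE "the deterioration of a pre-existing medical condition following or during exposure to a pharmaceutical product, whether or not considered causally related to the product", and among the forms an AE can take it lists "abnormal results of an investigation (e.g., laboratory findings, electrocardiogram".
- Section 6.2 begins "An SAE is an AE occurring during any study phase" and then lists the seriousness criteria. None of them turns on whether the underlying disease is the cause.
- Section 6.4 requires: "All SAEs must be reported, whether or not considered causally related to the IP, or to the study procedure(s".
- Section 6.3.8 covers asthma symptoms and signs, and has them recorded as AEs in several cases, the first being when "the sign or symptom is serious according to definitions, see Section 6.2".

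**The concern.** A site that sees a serious change in a scheduled laboratory test and is sure that asthma explains it receives opposite instructions. Section 6.4 says to report it, and 6.3.6 says not to. The same site, with a non-serious change that led to stopping the product, is told by the opening of 6.3.6 that this is one of the two kinds of change to report, and further down that it is not.

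The stake is where attribution takes place. Section 6.3.4 asks about causality after an event has been recorded, so an opinion that disease is responsible is kept and can be reviewed. The sentence in 6.3.6 applies that opinion before recording, so the event and the opinion both go unrecorded on the AE form. An event withheld in this way does not start the 24-hour notification in 6.4. It is also absent from the tables of SAEs and of AEs leading to discontinuation planned in 8.5.8.1.

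**Working it through.** The protocol gives no figure on this point, so the check is an enumeration. Take a deterioration in a protocol-mandated laboratory test and classify it by three yes/no facts: S, it meets a seriousness criterion in 6.2; D, it is the reason for stopping the product; P, it is unequivocally due to the disease. Apply the first paragraph of 6.3.6, then the disputed sentence, and compare the result with 6.4.

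| S | D | P | First paragraph of 6.3.6 | After the disputed sentence | Conflict |
|---|---|---|---|---|---|
| yes | yes | yes | report | withheld | 6.4, and first paragraph of 6.3.6 |
| yes | yes | no | report | report | none |
| yes | no | yes | report | withheld | 6.4, and first paragraph of 6.3.6 |
| yes | no | no | report | report | none |
| no | yes | yes | report | withheld | first paragraph of 6.3.6 only |
| no | yes | no | report | report | none |
| no | no | yes | not reported | not reported | none |
| no | no | no | not reported | not reported | none |

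Counting rows:

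1. There are 2 × 2 × 2 = 8 combinations. The first paragraph makes reportable those with S or D true, which is 8 − 2 = 6.
2. The sentence removes those of the six with P true, which is 3. All three are serious or treatment-stopping. Where neither holds, the sentence changes nothing, because the first paragraph has already excluded the change.
3. Two of the three removed combinations are serious and collide with 6.4. The third is outside 6.4, which governs SAEs only; its conflict is internal to 6.3.6.

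Could the conflict with 6.4 be avoided by saying that a disease-driven laboratory change is not an AE, and so cannot be an SAE? The definitions rule that out. Section 6.1 includes both the worsening of an existing condition and abnormal laboratory findings, whatever the cause, and 6.2 builds SAEs on that definition without a disease exclusion.

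These rows count kinds of event, not subjects. They show what the sentence can remove, not how often it would.

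**The case against.** The strongest case on the other side is that almost nothing falls under the sentence.

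- **The bar is high.** The link to disease must be unequivocal. A reader might infer that a rise in blood eosinophils, which is both a scheduled safety test and a listed exploratory biomarker, would be waved through as asthma. But if a blinded investigator cannot tell drug from disease, the change is not unequivocally disease and the sentence does not apply. This objection stands.
- **The clinical event is still captured.** A laboratory value seldom meets a seriousness criterion alone. Accompanying signs or symptoms are reported under 6.3.6, serious asthma signs and symptoms under 6.3.8, and hospitalisations as SAEs under 5.2.2.6. The liver-related stopping rules in 3.9.1 all involve raised transaminases, which are not a natural expression of asthma. This largely stands: what is lost is mainly the laboratory term.
- **The data are still analysed.** Section 8.5.8.2 plans summaries by treatment group, shift tables and plots, and 8.4.4.2 adds a sponsor review for other significant events. A reader might infer that a shift in one arm would go unseen, but these outputs do not depend on the AE form. They do not, however, replace notification of a serious event or its place in the SAE table.
- **Expedited reporting is hardly touched.** Section 3.7 ties code-breaking for that purpose to unexpected SAEs suspected to be caused by the product. An event judged to be wholly disease would not qualify.
- **Section 6.3.8 is not a contradiction.** It concerns symptoms and signs, and its discontinuation criterion is about leaving the study rather than stopping the product. It serves only as an analogy: where the protocol deals with disease progression directly, seriousness prevails over attribution to disease.
- **The sentence has a legitimate use.** It follows the rule on non-mandated parameters, where it keeps clinically relevant but disease-driven, non-serious changes off the AE form. This is a reason to amend it and not to delete it.

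None of these points removes the opposing instructions for the serious case.

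**Conclusion.** The sentence is wrong as written. For scheduled laboratory tests it can only withhold changes that are serious or that stopped the product. In the serious cases it contradicts 6.4 and the definitions in 6.1 and 6.2. In the non-serious, treatment-stopping case it contradicts the first paragraph of 6.3.6, and not 6.4.

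The practical effect is likely to be small, for the reasons just given. A reader might infer that several SAEs would vanish from the tables, enough to hide a signal. The protocol does not support this: it gives no rate of serious or treatment-stopping laboratory changes and no share attributed to disease, so no number of lost events can be derived.

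The conclusion rests on two assumptions. The first is that the opening paragraph of 6.3.6, which is phrased as a restriction, also states which mandated laboratory changes are to be reported; this matters only for the non-serious, treatment-stopping case, because 6.4 imposes the duty for serious ones. The second is that Appendix B, which 6.2 and 6.3.4 cite for guidance and which is not available here, does not already settle the matter.

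**What to change.** Reconcile 6.3.6 with 6.4 by keeping the sentence and adding an exception along these lines: *unless the change meets an SAE criterion or is the reason for stopping the investigational product*. Such changes are then reported, and a view that the disease is responsible is expressed through the causality question in 6.3.4. The exclusion of non-serious, disease-driven changes in non-mandated parameters that did not stop the product is unaffected. Appendix B should be checked for consistent wording.

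The cost is one clause in the protocol, a note to sites, and a few additional AE or SAE reports. No endpoint, sample size or efficacy analysis changes.
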